1.0 Research Design

1.1 Purpose/Specific Aims

The purpose of this project is to evaluate efficacy of Bright IDEAS, an evidence-based problem-solving skills training (PSST) program, as a supportive care intervention for adolescent and young adult (AYA) cancer patients compared with enhanced usual psychosocial care with 344 young adult patients newly diagnosed with cancer.

A. Objectives

We will evaluate the efficacy of Bright IDEAS-YA by examining changes in psychosocial outcomes from baseline to post-intervention (3 months) and follow-up (6, 12, and 24 months).

We will determine the extent to which changes in aspects of problem-solving ability mediate the intervention effects and examine relevant moderators.

B. Hypotheses / Research Question(s)

Aim 1: Evaluate the efficacy of Bright IDEAS-Young Adults on psychosocial outcomes.

Hypothesis 1: Participants who receive the Bright IDEAS-YA intervention will report lower depression, anxiety, and impairment in health-related quality of life over time than participants who receive usual psychosocial care.

Aim 2: Determine the extent to which problem-solving ability mediates treatment effects.

Hypothesis 2: The effects of the intervention will be mediated by improved positive problem orientation and rational problem-solving skills, and reduced negative problem orientation, impulsive style, and avoidant style.

Aim 3 (Exploratory): Examine moderators of treatment effects.

Sex, financial strain, and baseline unmet needs will be examined as potential moderators of treatment effects to identify subgroups who benefit most from this intervention.

1.2 Research Significance

Young adults with cancer diagnosed between the ages of 18 to 39 are increasingly recognized as a vulnerable group with unique emotional, social, and practical needs due to the intersection of cancer treatment and normal developmental processes.¹ Although a cancer diagnosis at any age is highly stressful, cancer diagnosis and treatment during the critical period of young adulthood is particularly challenging. A cancer diagnosis during this time can hinder the process of achieving desired developmental tasks in all life domains, including identity, education, career, financial independence, relationships, and starting a family.²,³ These disruptions put young adults at particularly high risk of negative outcomes due to their underdeveloped problem-solving ability (i.e., capacity to find effective solutions to problems) and limited resources (i.e., less experience dealing with similar challenges, unstable social support). Ongoing concerns and unmet informational, emotional, and practical support needs are associated with increased emotional distress and poorer health-related quality of life.²,⁴ A critical gap in the field is the lack of evidence-based interventions to address the unique concerns of the young adult population.

To address this clinical care gap, a behavioral intervention is needed that provides skills to manage the diverse and numerous stressors associated with a cancer diagnosis in the context of life transitions, addresses underdeveloped problem-solving ability characteristic of this age group, and is relatively simple to learn and use during the highly stressful time following cancer diagnosis. Problem-solving skills training is uniquely suited to fit this need, as it teaches a global life skill to help young adults address *any* concern, is tailored to individual needs, and is relatively simple to learn and use. Problem-solving skills training is an application of problem-solving therapy, which has accumulated a large body of evidence showing it successfully improves problem-solving ability, reduces negative affect, and improves health-related quality of life. 5678-1112-1516 17138

1.3 Research Design and Methods

Bright IDEAS-YA will be tested with young adult cancer patients in a two-arm parallel randomized controlled trial (RCT) of the intervention versus enhanced usual psychosocial care.

A. Research Procedures

Research staff will collect participants' contact information for tracking and study management. Following consent, baseline surveys (see section 1.9 Data Collection) will be administered online using DatStat, a HIPAA-compliant electronic data capture system. Research staff will either provide a tablet for patients to complete the online survey (paper copies will be available as back-up in the event of significant internet disruption) or email/text a link for completion. If a participant does not complete the baseline survey during an initial in-person visit, we will email a link for completion. After completion of the baseline survey, participants will be randomly assigned 1:1 to either the intervention or enhanced usual psychosocial care comparison group. The study biostatistician will determine a randomization scheme stratified by site, age group (18-29 vs. 30-39 based on definitions of emerging adults and young adults¹⁸)using an undisclosed block size to balance group assignment within each site and age group. This schema will be uploaded to the DatStat program such that completion of the baseline survey will trigger assignment according to the schema via a message to study staff. Participants will then be notified of assignment via an automatic Welcome email through DatStat. For those assigned to the intervention group, study staff will assign a Bright IDEAS-YA trainer, schedule for the participant and trainer to meet at the patient's next medical visit or schedule a virtual meeting to complete the first Bright IDEAS-YA session, and mail/email Bright IDEAS-YA manual, worksheets and the list of resources from the NCCN adolescent and young adult patient guildeline. 19 For those assigned to the enhanced usual psychosocial care group, study staff will mail/email the list of resources from the NCCN adolescent and young adult patient quidelines. 19 All participants will also be mailed a small gift (e.g., Bright IDEAS stress ball) as a token of appreciation for their time and effort. Trainers will schedule all subsequent sessions directly with participants. All participants will be asked to complete surveys at 3 months (post-intervention), 6 months (3-month follow-up), 12 months (9-month follow-up), and 24 months (21-month followup). DatStat will send survey links and subsequent reminders via email/text according to the survey schedule. Study staff will also call and/or send text message reminders to participants to facilitate completion of online surveys as needed. All participants will continue to receive usual psychosocial care per institutional standards, as well as a standardized list of young adult-specific resources (see Enhanced Usual Psychosocial Care section). Usage of these services will be tracked via patient self-report at each survey. Participants will receive \$25 for each of the first four surveys completed, and a \$50 gift card for completing the final survey (up to \$150 total).

B. Data Points

All participants will be asked to complete follow-up surveys at 3 months (post-intervention), 6 months (3-month follow-up), 12 months (9-month follow-up), and 24 months (21-month follow-up). Study staff will also collect data regarding participant completion of intervention sessions and trainer fidelity. Intervention sessions will be audio-recorded with participant permission for fidelity evaluation and trainer supervision.

C. Study Duration

The overall study will last 5 years. Each subject will participate for 2 years.

D. Endpoints

The primary endpoint will be the estimated change from baseline to 6 months in depression, anxiety, and psychosocial HRQOL (i.e., Social/Family Well-Being and Emotional Well-Being), selected to allow for examination of temporal mediation of problem-solving ability post-intervention. The changes from baseline to 3 months, 12 months, and 24 months will be considered secondary endpoints.

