1.5 Sample Size Justification

Up to 344 YA patients newly diagnosed with cancer will be enrolled across sites. There are no exclusion criteria based on gender or race. We expect the percentage of male/female and minority race participants enrolled to reflect the distributions seen at three sites.

Power focused on Aim 1 and was calculated based on effect size estimates that incorporate both estimates of change in mean as well as standard deviations from our pilot data and compared against published data, assuming an intent-to-treat analysis. For the proposed study, we assume the standard deviation will be 70% of the pilot standard deviation, due to tightening of the eligibility criteria to exclude those with cancer recurrence and recruit within 4 months of first diagnosis. In addition, we assume that the control group will see 20% of the change in depression compared to intervention. This leads to a Cohen effect size of 0.26. Assuming 344 subjects with 30% dropout, we will have 85% power to detect an effect of intervention on the Depression score. Similar calculations demonstrate 82% power to detect an effect of intervention on Anxiety. If we observe a group difference closer to 3.22 for Depression, cited as clinically meaningful in previous literature,²³ then under the assumptions listed above, our Cohen effect size will be closer to 0.29 and our power for the primary outcomes will be higher. For HRQOL, pilot Cohen estimates of effect size and estimates from the literature with the assumptions above would yield a Cohen effect size of 0.32, which would yield a power of 95%.²⁴²⁵

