4.0 Subject Considerations

4.1 Subject Selection and Enrollment Considerations

A. Method to Identify Potential Subjects

At each site, patients will be identified through electronic medical record review of active patients and by referrals from treating physicians/nurses/social workers. Research study staff will contact treating physicians or other qualified treatment team member familiar with the patients, to assess

medical eligibility of patients. If a physician or other treatment team member feels their patient is not suitable for participation, we will not approach the patient. Patients who pass initial screens will be approached in person by research staff during a routine medical visit or contacted by letter/phone or email (if available).

B. Recruitment Details

Trained research staff will approach potentially eligible patients during a routine medical visit or via letter/phone, or e-mail (if available). If in-person, study staff will hand out the study information sheet and flyer, explain the study, assess interest/eligibility, allow adequate time for review and discussion with family if needed, and obtain informed consent if patient is eligible and interested. If by letter/phone, study staff will mail study cover letter along with the study information sheet and flyer to explain the study and let them know they will be contacted by phone by a member of the study team to assess interest and eligibility. If patient's email address is available, an email will be sent to introduce the study and to let them know the study staff will follow-up with a phone call. Staff will be rigorously trained as to how to approach patients, introduce the study, communicate about confidentiality and voluntary participation, and engage in the process of informed consent in a culturally-competent way.³⁹ Recruitment scripts, cover letter, information sheet, e-mail wording and flyer are being uploaded for approval.

C. Subject Screening

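### Withholding the block size is the only stated guard against predicting assignments from the blocks; randomly varying sizes would remove most of the certainty a single size could give

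*Combined protocol and SAP*

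**What the plan says.** Section 1.3 A (Research Procedures) states that "participants will be randomly assigned 1:1 to either the intervention or enhanced usual psychosocial care comparison group". The biostatistician prepares the scheme, "stratified by site, age group (18-29 vs. 30-39"), "using an undisclosed block size to balance group assignment within each site and age group". It is loaded into DatStat, and "completion of the baseline survey will trigger assignment according to the schema via a message to study staff". For the intervention arm, "study staff will assign a Bright IDEAS-YA trainer", arrange the first session and send the arm's materials.

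The surrounding sections show who sees and does what:

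- Section 1.9 (Internal Tracking): each site's Research Assistant registers and tracks all participants at that site.
- Section 2.1: research assistants deliver the intervention.
- Section 4.1 B: "Trained research staff will approach potentially eligible patients during a routine medical visit or via letter/phone, or e-mail (if available").
- Section 4.4 A: the PI, coordinator or a trained research staff member obtains consent.

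No section says that block sizes vary, that recruiting staff are kept from seeing assignments, or that recruiting and receiving assignments are separate jobs.

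**The concern.** Blocking forces the arms to balance at the end of every block. Someone who knows the block size and sees each past assignment in a stratum therefore knows the last assignment of every block, and sometimes the last few. Site staff see the whole sequence in their own two age strata. If one size is used throughout, keeping it unprinted delays recognition but does not prevent it.

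Randomisation happens only when the baseline survey is complete, and that survey may be finished later from an emailed link. A staff member who expects a particular arm could time an approach, or chase an unfinished survey, accordingly. Because research assistants also run sessions, the next arm bears on staff workload. Selection of this kind acts before randomisation, so an intent-to-treat analysis does not remove it. Adjustment for baseline imbalance appears in Section 6.1 only as a sensitivity analysis, and it can deal only with measured characteristics.

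**Working it through.** The documents give no block size and no predictability figure, so there is nothing to reproduce. Block sizes below are assumptions, shown as a range.

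**Inputs.** Allocation is 1:1, by site and two age groups (Section 1.3 A). The total is 344 ("Up to 344 YA patients newly diagnosed with cancer will be enrolled across sites", Section 1.5). There are three sites (enrolment is expected to "reflect the distributions seen at three sites", Section 1.5). Strata: 3 × 2 = 6. If equal, which is an assumption, each stratum has 344/6 ≈ 57 patients and each site 344/3 ≈ 115.

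**Step 1: ceiling, with one size known from the first patient.** In a block of b = 2m, the certain assignments are the closing run of identical ones. Its expected length is the sum over k = 1 to m of 2·C(b−k, m−k)/C(b, m).

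- b = 4: 1 + 1/3 = 1.333; 1.333/4 = 33.3%
- b = 6: 1 + 0.4 + 0.1 = 1.5; 1.5/6 = 25.0%
- b = 8: 1 + 0.429 + 0.143 + 0.029 = 1.6; 1.6/8 = 20.0%

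The share reduces to 1/(m+1).

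**Step 2: recognition time.** The simulated observer is ideal. It pools a site's two strata, starts with equal prior weight on fixed sizes 2, 4, 6, 8 and 10, and stops when the true size passes 95% posterior probability. The median is 40, 32 or 24 patients for blocks of 4, 6 or 8. Only the remainder of the site's 115 or so is then exposed:

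- b = 4: 33.3% × 75/115 ≈ 22%
- b = 6: 25.0% × 83/115 ≈ 18%
- b = 8: 20.0% × 91/115 ≈ 16%

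**Step 3: randomly varying sizes.** This step simulated 2,000 strata of 57, with an observer who knows the set of sizes from the start but not their order.

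**Step 4: best guess.** The observer guesses the likelier arm each time. For b = 4 the expected number correct is 1/2 + 2/3 + 2/3 + 1 = 2.833, so 2.833/4 = 70.8%. Chance is 50%.

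| Scheme | Certain share | Of 344 | After recognition period | Best guess correct |
|---|---|---|---|---|
| Fixed 4 | 33.3% | 115 | about 22% | 70.8% |
| Fixed 6 | 25.0% | 86 | about 18% | 68.3% |
| Fixed 8 | 20.0% | 69 | about 16% | 66.6% |
| Random 2/4 | 10.9% | 37 | not discounted | 71.8% |
| Random 4/6 | 5.5% | 19 | not discounted | 68.8% |
| Random 4/6/8 | 2.5% | 8 | not discounted | about 67.5% |

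The fixed rows assume complete blocks. In simulated strata of 57, where the last block is cut short, fixed 4 and 6 gave 32.8% and 23.7%.

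**The case against.** A reader might infer that the trial uses one fixed block size. The text does not say so. The singular wording suggests it, but the plan neither calls the size fixed nor excludes variation, and holding back blocking details is itself a concealment measure.

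A reader might also infer that a fifth to a third of assignments are known to staff. That is a ceiling, requiring knowledge of the size from the first patient. Even the lower figures assume formal inference from stratum-by-stratum tallies by an observer who takes the size to be fixed. Nothing in the documents suggests that staff keep such tallies.

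Foreknowledge is also not control. Section 1.9 A allows the survey to be completed at home or on mailed paper, so with several consented patients pending, staff do not fully determine who takes the next place. Section 4.1 A gives the treating team a say in who is approached. The recipients of assignments and the recruiters share labels such as study staff and research staff, but no section says they are the same individuals. The workload motive is conjecture, and no manipulation is shown.

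Finally, varying sizes barely change best-guess accuracy. If the undisclosed size is 8, a random 4/6/8 scheme raises it slightly, from 66.6% to about 67.5%.

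All of this stands, and it limits the size of the point. It does not remove it: the plan names no safeguard against block prediction beyond non-disclosure, and a better method is available at little cost.

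**Conclusion.** The point holds as a low-severity improvement. If one block size is used and comes to be inferred, at most 20% to 33% of assignments are certain, and roughly 16% to 22% (about 54 to 75 of 344) after an ideal observer's recognition period. These figures rest on block sizes of 4 to 8, equal sites and strata, and staff who see every assignment in their strata. Randomly varying sizes reduce certainty to about 2.5% for a 4/6/8 mix and 5.5% for 4/6, even against an observer who knows the set of sizes. The benefit is removal of most certain knowledge; the sequence does not become unpredictable.

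The documents do not support a finding that allocation concealment has failed or that outcomes are biased. The schema is prepared by the biostatistician, release is automated, and each assignment follows consent and baseline. No bias in any endpoint has been estimated here.

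**What to change.** In Section 1.3 A, replace the reference to one block size with, for example: *Assignments not yet made will use permuted blocks whose size varies at random within each site and age group. The sizes and their order are held only by the study biostatistician and within DatStat.* Do not print the sizes. If they already vary, a sentence saying so is enough. The set matters: in the table, a 2/4 mix still leaves 10.9% certain.

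The cost is a regenerated and reloaded list and a minor protocol modification. The largest imbalance from an unfinished block is half its size, so moving from a fixed 4 or 6 (2 or 3 patients) to a mix with a maximum of 8 (4 patients) adds at most one or two per stratum. Finishing the open block in each of the six strata before switching avoids cutting blocks short. Sample size and the analysis model are unchanged.

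The documents do not give recruitment status. If enrolment is complete, the useful step is to document the scheme that was used and who could see the assignments.

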1.6 Study Variables

A. Independent Variables, Interventions, or Predictor Variables

Bright IDEAS-YA Intervention: Bright IDEAS-YA is a manualized problem-solving skills training intervention conducted by a trainer who teaches the participant the Bright IDEAS stepwise approach to problem-solving and guides the participant through solving their own problems using the Bright IDEAS approach and worksheets. The intervention consists of six 45-minute one-on-one sessions held at the clinic/hospital, by telephone between a patient and a trainer, or via video-conference session on HIPPA compliant Doxy.me (https://doxy.me/), or another institutionally-approved telehealth platform (e.g. Rutgers Zoom, site-specific telehealth platforms). Sessions are held weekly. However, due to the changing demands of cancer treatment and side effects that sometimes cause patients to feel too ill to do a session as scheduled, we allow up to 12 weeks to complete the 6

sessions. During the first face-to-face or virtual session, participants will be introduced to the Bright IDEAS model and the participant manual that explains the approach and provides worksheets for systematically solving problems. "Bright" refers to the sense of optimism that is critical to finding constructive solutions to difficult challenges. The letters in IDEAS represent the five essential steps of the PSST problem-solving approach (see Figure 1): "I"= "Identify the problem"; "D"="Determine the options"; "E"="Evaluate options and choose the best"; "A"="Act"; and "S"="See if it worked." Sessions 2-5 involve using the model to work through challenges identified by the participant. Session 6 involves a summary of the model, discussion of how the participant can continue to use the skills learned after the sessions end, and solicitation of feedback regarding the program and the website/app. See Table 1 for overview of each session.

Table 1. Overview of Bright IDEAS-YA Intervention Sessions

1. Overview of Bright IDEAS-TA Intervention Sessions										
Session	Goals/Activities Mapping to Problem-Solving									

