6.0 Data Management Plan

6.1 Data Analysis

Aim 1: Efficacy of the Bright IDEAS-YA intervention vs. enhanced usual psychosocial care will be evaluated assuming repeated measures linear models, using maximum likelihood estimation (MLE) (SAS Proc Mixed).⁴⁰ All randomized participants, regardless of the extent to which they completed the intervention, will be included in intent-to-treat analysis. The benefits of this approach include: (1) all available data can be included in analyses; (2) correlation between related measures and adjusted test statistics can be estimated; (3) time varying covariates (such as school/employment status, treatment status (on treatment vs. completed), utilization of usual psychosocial care) can be incorporated into the model; and, (4) the assumptions about missing data from Missing Completely at Random (MCAR) to Missing at Random (MAR) are relaxed. Site will be included as a fixed effect. The primary hypothesis is that participants in Bright IDEAS-YA will experience greater decreases in depression and anxiety and increases in HRQOL at the 6month follow-up relative to participants in the enhanced usual psychosocial care condition. The primary endpoint will be the estimated change from baseline to 6 months in depression, anxiety, and psychosocial HRQOL (i.e., Social/Family Well-Being and Emotional Well-Being), calculated as linear contrasts of regression parameters using the main effect of time and the interaction between time and treatment group from the mixed linear model. The changes from baseline to 3 months, 12 months, and 24 months will be considered secondary endpoints. For HRQOL, we are particularly interested in 12-and 24-month followups given that changes may take longer to accrue compared with distress symptoms. Sensitivity analyses will be performed to determine the robustness of conclusions.⁴¹ Planned sensitivity analyses include: (1) analysis with and without adjusting for site; (2) per protocol analysis (excluding participants who did not complete at least 4 out of 6 intervention sessions, selected because it is expected that participants would have adequate exposure and practice with the Bright IDEAS model by four sessions); (3) adjustment for imbalance in baseline characteristics, if applicable; and (4) analysis to examine any differences by racial/ethnic subgroups.

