Aim 2: Mediation analysis will be used to evaluate problem-solving ability as a mediating variable between the intervention and each of the outcomes while also allowing for a direct effect of intervention on outcome. Specifically, bootstrap approaches will estimate the proportions attributed to the direct effect and to the effect mediated through problem-solving using the R program package mediation.⁴²

A small direct effect is expected due to a positive therapeutic effect of talking to the trainer. Problem-solving ability will be measured by the total scale score and five subscales (positive problem orientation, negative problem orientation, rational problem solving, impulsive-careless style, and avoidant style), which will each be considered individually as potential mediators.

Aim 3: Potential moderators, including sex, financial strain, baseline unmet needs, and baseline distress, will be tested individually in models including all possible interaction terms. We will allow for each moderator to interact with time, arm, and time x arm to determine if it modifies the relationship between intervention and outcomes. We consider this analysis exploratory to identify subgroups who may benefit differentially from this intervention. We expect that females and participants with greater financial strain, baseline unmet needs, and baseline distress will benefit more.

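### The primary model has no term for trainers, who are shared within the intervention arm only; if outcomes vary by trainer, the standard error of the 6-month contrast is too small.

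*Combined protocol and SAP*

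**What the plan says.** Section 1.3 states that, for participants randomised to the intervention, "study staff will assign a Bright IDEAS-YA trainer". Section 1.6 describes the delivery: "The intervention consists of six 45-minute one-on-one sessions". The comparison arm completes surveys, receives the NCCN resource list and continues usual psychosocial care, with no trainer. Section 3.0 says that trainers are personnel hired by each site, and section 1.5 refers to three sites. Section 2.1 adds that trainers need not be professional counsellors.

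For the primary analysis, section 6.1 (Aim 1) specifies a repeated-measures mixed model fitted by maximum likelihood. The baseline-to-6-month contrast is built from time and time-by-arm terms, and time-varying covariates are allowed. The only term that reflects how participants are grouped is site: "Site will be included as a fixed effect". The four planned sensitivity analyses concern site, per-protocol status, baseline imbalance and racial/ethnic subgroups. None concerns trainers.

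The sample size section (1.5) gives no ICC, design effect or number of trainers.

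**The concern.** This is a partially nested design: participants are grouped under trainers in one arm and are ungrouped in the other. If trainers differ in the outcomes that they achieve, two participants of the same trainer are correlated. The intervention-arm mean then carries a between-trainer component that does not shrink as participants are added under the same trainers. A model that correlates only the repeated measures within a participant leaves that component out of the standard error of the arm difference.

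The contrast affected is the primary one, and the same model serves depression, anxiety and psychosocial HRQOL. At stake are a confidence interval that is too narrow and a test that rejects more often than its nominal level, under the null hypothesis that the programme has no average effect across trainers of this kind.

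**Working it through.** **Inputs from the documents.** 344 randomised 1:1, so 172 per arm; 30% dropout (section 1.5), so 344 × 0.70 ≈ 241 analysed, about 120 per arm. Depression: effect size 0.26, power 85%.

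**Assumed, because not stated.** Two-sided alpha of 0.05; 4 to 12 trainers with equal caseloads; trainer ICC of 0.01 to 0.05, defined on the 6-month change.

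**The plan's power figure.** A plain two-sample comparison with d = 0.26 and 120.4 per arm has noncentrality 0.26 × √(120.4/2) = 2.017, hence power Φ(2.017 − 1.96) ≈ 52%. With 172 per arm it is 67%. The stated 85% is therefore not reproduced by this formula. It is reachable with an unstated baseline-to-follow-up correlation of about 0.74 (baseline-adjusted) or 0.77 (change score). The HRQOL figures (0.32, 95%) imply nearly the same, 0.72 or 0.76. A repeated-measures calculation is thus plausible, and 85% is taken below as the starting point. No listed input allows for trainers.

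**Effect of ignoring trainers.** With m = 120/k participants for each of k trainers:

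- intervention-arm design effect DE = 1 + (m − 1) × ICC; control arm 1;
- true SE / naive SE: R = √((1 + DE)/2);
- naive SE too small by 1 − 1/R;
- actual type I error = 2 × Φ(−1.96/R).

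Upper end (4 trainers, ICC 0.05): m = 30; DE = 1 + 29 × 0.05 = 2.45; R = √1.725 = 1.313. The true SE is 31% larger than the naive one, so the naive SE is 1 − 1/1.313 = 24% too small. Type I error = 2 × Φ(−1.492) = 13.6%.

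Lower end (12 trainers, ICC 0.01): m = 10; DE = 1.09; R = √1.045 = 1.022. The naive SE is 2.2% too small and the type I error is 5.5%.

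| Trainers (m) | ICC 0.01 | ICC 0.02 | ICC 0.05 |
|---|---|---|---|
| 4 (30) | 6.7% | 8.4% | 13.6% |
| 6 (20) | 6.1% | 7.2% | 10.7% |
| 12 (10) | 5.5% | 6.0% | 7.7% |
| 20 (6) | 5.3% | 5.6% | 6.5% |

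With all 172 per arm analysed, caseloads are larger and the range for 4 to 12 trainers becomes 5.8% to 17.1%.

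**Does the site term help?** Change scores were simulated with three sites, 120 per arm, site as a fixed effect and no trainer term (4,000 runs per setting). Type I error was 4.7% to 5.2% at ICC 0. At ICC 0.05 it was 17.2% with 3 trainers, 10.1% with 6 and 7.0% with 12. These agree with the formula (16.3%, 10.7%, 7.7%), so adjusting for site does not remove the inflation.

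**Does a nested analysis help?** In a second simulation (6,000 trials per setting), type I error without and with trainer nesting was 13.0% and 6.0% (4 trainers, ICC 0.05), 6.8% and 5.1% (6 trainers, ICC 0.02), and 7.4% and 4.7% (12 trainers, ICC 0.05).

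**Power once trainers are modelled.** The stated 85% implies noncentrality 1.96 + 1.036 = 2.996. At ICC 0.05:

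- 12 trainers: R = √1.225 = 1.107; 2.996/1.107 = 2.707; power Φ(0.747) = 77%, or 75% with Satterthwaite degrees of freedom (about 30).
- 6 trainers: R = √1.475 = 1.214; 2.996/1.214 = 2.467; power Φ(0.507) = 69%, or 62% with Satterthwaite degrees of freedom (about 11).

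**The case against.** The strongest reply is that the documents do not show that trainers differ. A reader might infer such differences from the Aim 2 text: "A small direct effect is expected due to a positive therapeutic effect of talking to the trainer". That sentence describes an average effect of contact and says nothing about variation between trainers. Likewise, the treatment-integrity checklist in section 1.9 rates alliance and fidelity as a check on uniform delivery; it is not evidence of heterogeneity. The manual, standardised training with role play and regular supervision (sections 1.6, 2.1 and 3.0) are meant to make trainers alike, and they make the upper end of the assumed ICC range less likely. This stands as a limit on size. It does not replace an adjustment, and the plan gives no reason to take the ICC as zero.

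Second, sharing of trainers is inferred. Section 1.3 shows assignment only, and section 3.0 allows further personnel to be trained, so caseloads could be small. The intent-to-treat set also includes participants with few or no sessions, which dilutes clustering. Still, with about 172 participants and staff hired by site, some sharing is hard to avoid.

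Third, if inference is confined to the trainers actually employed, trainer effects are fixed and the inflation argument does not apply. Nor is there inflation under the strict null in which no trainer has any effect. Treating trainers as random is a choice of inference population. It is a natural one for a manualised programme tested for efficacy, but the plan should state it.

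Fourth, the remedy is imperfect when trainers are few. The variance component is then poorly estimated, the nested test still ran at 6.0% with 4 trainers, and with one trainer per site trainer cannot be separated from site-by-arm. This stands and shapes the fix.

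**Conclusion.** The omission is real: section 6.1 has no trainer term, trainer-clustered standard error or trainer sensitivity analysis, and the site effect does not substitute for one. The consequence is conditional. For any positive trainer ICC with shared trainers, the standard error of the 6-month contrast is too small when inference is meant to extend beyond the trainers employed. Under the assumed 4 to 12 trainers, ICC 0.01 to 0.05 and 120 analysed per arm, it is about 2% to 24% too small and the nominal 5% test runs at about 5.5% to 13.6%. With 20 trainers and ICC 0.01 the rate is 5.3%, which is negligible; at ICC 0 there is no inflation. Confidence in the omission and its direction is high. Confidence in the size is low, because neither driving figure is given.

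Two stronger readings are not supported. One is that the trial's type I error is known to be inflated, or that a positive result would merely reflect a few good trainers; the documents contain no evidence of differences between trainers. The other is that the stated 85% power is wrong because a simple formula gives 52%; a repeated-measures calculation could reach it, and that question is separate from this one.

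**What to change.** 1. Record the trainer ID for every intervention participant. It is known at assignment.
2. Pre-specify in section 6.1 a partially nested analysis: a trainer random effect on post-baseline visits in the intervention arm only, controls unclustered, with Satterthwaite or Kenward-Roger degrees of freedom. Report the estimated trainer ICC.
3. Before outcome data are examined by arm, state the number of trainers. If there are enough of them, make this the primary model; otherwise add it as a named sensitivity analysis. Add it alongside the existing analysis with and without site, not in place of it.
4. State that with one trainer per site, trainer cannot be separated from site-by-arm.
5. Give the expected number of trainers and an assumed ICC in section 1.5.

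The cost is analysis wording and one recorded field. If the trainer variance is estimated as zero, the fit reduces to the current model. If the ICC is positive, the interval widens: starting from the stated 85%, power at ICC 0.05 would be about 75% to 77% with 12 trainers and 62% to 69% with 6.
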